9. DATA ANALYSIS/STATISTICAL METHODS

9.1 Sample Size Determination

The primary objective of this real-world study is to demonstrate that locally therapy during 1L lorlatinib is instrumental in prolonging TTD by investigator assessment per RECIST v1.1.

Approximately 100 patients who receive lorlatinib in first line are expected to be included in this study. Since this study is descriptive without specified hypothesis, the sample size is not determined based on statistical assumptions, but according to the following information: epidemiology, China marketing competition environment, marketing research report, drug availability, patient affordability, health insurance coverage, and at least 20% dropout rate. Comprehensively, the final sample size of this study is expected to reach for about 100 cases.

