first-line resistance mechanism of lorlatinib is still ambiguous,²³ the sequencing therapy after PD of first-line lorlatinib is far from definite, and how lorlatinib benefiting ALK-positive NSCLC patients in clinical practice beyond CROWN criteria should be further explored. There is no clear answer so far to these clinically relevant questions.

In addition, recent clinical studies have shown that continuation of TKI treatment beyond progression in patients with oligometastasis NSCLC can be an effective strategy to target tumor cells that still addicted to the EGFR pathway and prevent the disease flare observed after discontinuation of the targeted agent.^{24,25} Further more, for patients with oligometastases (means target lesions with residual disease, definition a maximum of 3 organs, and no more than 5 lesions in total), treatment should be considered in combination with local therapeutic approaches, such as surgery, local ablation or radiotherapy, to improve disease control and thereby long-term survival outcomes.²⁶ However, no studies have yet reported whether patients with ALK+ NSCLC can also benefit from the above treatment mode.

This real-word study is designed to prospectively explore whether local treatment (surgery, ablation, radiotherapy and others) can prolong the time to treatment discontinuation during 1L lorlatinib treatment in Chinese patients with unresectable ALK⁺ NSCLC. Since this is a non-interventional study (NIS) to observe the routine practice, there will not be any study required clinical interventions or laboratory assessments. Participation in this study is not intended to change the routine treatment received as determined by their attending physicians. Patients will be treated according to the routine medical practice in terms of visit frequency and types of assessments performed.

This study will enroll patients with ALK-positive non-small cell lung cancer locally diagnosed in about 6 sites in China from study setup to about Oct 2025, as the target observation population. Patients' effectiveness and safety data of first line treatment with lorlatinib will be collected after their first dose until the 60th month or patient death, loss to follow-up, or withdrawal from the study for any reason. The visit schedule

during study is not mandatory and follow local routine clinical practice.

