2. STUDY OBJECTIVES

2.1. Objectives

Primary Objective:

- To evaluate the time-to treatment discontinuation (TTD) of lorlatinib with locally therapy in unresectable ALK-positive NSCLC patients who have received 1L lorlatinib in real-world settings;

Secondary Objectives:

- To evaluate the rwORR, rwDCR and real-world intracranial ORR, intracranial time to progression (IC-TTP) and TTP of 1L lorlatinib in real world setting ;
 - To explore the progression pattern in this therapeutic changing mode;
- To evaluate 1/2/3/4/5-year overall survival (OS) rate and OS of in each treatment cohort;
- To explore the association between the effectiveness of lorlatinib in first line for Chinese patients with ALK-positive locally advanced or metastatic NSCLC patients with baseline brain metastases (Yes or No) , ALK Fusion Variants ([V1, V2, V3] and

TP53 mutation status [TP53 mutation, TP53 WT]) if data is available in medical records;

- To evaluate the safety and tolerability of the therapeutic changing mode;
 - To explore the adverse events (AEs), the dose modification and the reason for interruption or discontinuation of lorlatinib in first line for Chinese ALK-positive locally advanced or metastatic NSCLC recorded in medical records;
 - To evaluate patient-reported outcomes (PROs) of health-related quality of life for this therapeutic mode;
 - To describe the demographic, clinicopathological and baseline co-mutation characteristics of enrolled patients.

Exploratory Objectives:

- To explore dynamic ctDNA change during lorlatinib treatment;
- To evaluate candidate biomarkers of sensitivity or resistance to lorlatinib in no-prior ALK-TKIs treatment tumor tissue and peripheral blood if available in real world setting;

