9.2 Effectiveness Analysis

9.2.1 Analysis Populations

The following subject populations will be assessed:

Safety-Analysis-Set (SAT) Population

The SAT Population will include all subjects who receive at least 1 dose of study medication. The SAT Population will be the primary population for evaluating treatment administration/compliance and safety.

Censoring for time-to-event efficacy endpoints (i.e., PFS and OS) will be elaborated in the SAT.

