9.2.3 Analysis of Primary Endpoint

TTD will be summarized using Kaplan-Meier methods and displayed graphically. Potential influences of other demographic baseline characteristics including biomarker profile use parametrical test, χ^2 or Fisher exact test .

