9.2.5 Analysis of Secondary Endpoints

rwPFS, IC-TTP and Overall Survival will be summarized using Kaplan-Meier methods and displayed graphically. The 1/2/3/4/5-year rwPFS, IC-TTP and survival probability will be estimated using Kaplan-Meier methods and the 2-sided 95% CI will be provided. Potential influences of other demographic, baseline characteristics including biomarker profile use parametrical test, χ^2 or Fisher exact test. Objective Response Rate will be summarized for the SAT Population based on the investigator's assessment. The number and percent of subjects achieving objective response (CR or PR) will be summarized along with corresponding 2-sided 95% CI using the binomial distribution.

Intracranial Objective Response Rate will be summarized for the SAT Population based on the investigator's assessment. The assessment of intracranial response will be conducted on subjects with measurable and unmeasurable CNS metastases. The number and percent of subjects achieving objective response (CR or PR) will be summarized along with corresponding 2-sided 95% CI using the binomial distribution.

Subgroup analysis is considered to be conducted by baseline characteristics such as CNS (Yes/No), TP53 status (Yes/No), ALK-EML4 fusion variant (V1, V2, V3) in patients with baseline who receive lorlatinib in first line. Depending on the actual sample size at the time of analysis, adjustment by either combining or re-classifying the subgroups will be applied as needed.

Subgroup comparisons, where is applicable, will be performed using the Kaplan-Meier method and the log-rank test. Statistically significant level of $\alpha=0.05$ (two sides) is used for tests.

The qualitative exploratory endpoints will be categorized and summarized descriptively by count and percentage of patients. Missing data will be categorized by missing, unknown, or can't be determined.

The interim analysis will be performed when the completion of 2.5 year follow-up in late patient. The final full analysis will take place at the time of data cut-off (i.e. the completion of 60-month follow-up for all the participants).

Descriptive statistics will be used to summarize subject characteristics, study conduct, subject disposition, treatment administration/compliance, and safety parameters. Data will also be displayed graphically, where appropriate.

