will be done for each site to validate generalizability of outcomes respective of geographic location of the participants. Furthermore, disease assessment will be based on evaluations performed by the attending physicians in real-world clinical practice. Although a significant proportion of physicians use RECIST in their clinical practice, it may still result in an inconsistent definition of tumor response and disease progression. Such information bias can be minimized to some extent by following a well-designed data management process and through appropriated definition of variables to sufficiently use available information. Lastly, no hypotheses will be tested in this study and only descriptive analysis will be performed. Thus, results cannot serve as a general conclusion on the effectiveness and safety of lorlatinib.

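### Section 9.1 sets out to demonstrate that local therapy prolongs TTD, but the study is declared descriptive and the readable text plans no TTD contrast by local therapy

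*Protocol*

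**What the plan says.** The protocol words its primary aim in several ways.

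- Section 9.1, first paragraph: "to demonstrate that locally therapy during 1L lorlatinib is instrumental in prolonging TTD".
- Section 9.1, second paragraph: "Since this study is descriptive without specified hypothesis, the sample size is not determined based on statistical assumptions".
- Section 10.2, limitations text: "no hypotheses will be tested in this study and only descriptive analysis will be performed".
- Section 2.1: to evaluate the "time-to treatment discontinuation (TTD) of lorlatinib with locally therapy".
- Section 1: to "prospectively explore whether local treatment (surgery, ablation, radiotherapy and others) can prolong the time to treatment discontinuation".

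On the analysis, Section 9.2.1 defines one population: "The SAT Population will include all subjects who receive at least 1 dose of study medication". Section 9.2.3 reads: "TTD will be summarized using Kaplan-Meier methods and displayed graphically", followed by unspecified influences of baseline characteristics. Section 9.2.5 adds: "Subgroup analysis is considered to be conducted by baseline characteristics such as CNS (Yes/No), TP53 status (Yes/No" and fusion variant, compared by log-rank test at two-sided 5%.

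Local therapy is not a baseline factor. Under Sections 3.1 and 6.2.4 it is considered only after target lesions have been stable on two consecutive scans on lorlatinib. Under 3.1, patients in complete response or with multiple metastases receive none. TTD (9.2.2) and OS (9.2.4) both run from the start of treatment.

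**The concern.** *Demonstrate* and *prolong* are comparative and confirmatory words. They need a group with local therapy, a group without it, and a contrast between them. The protocol disclaims hypothesis testing twice, and its readable text supplies no such contrast for TTD. A single curve has no comparator. Nor does it give TTD with local therapy, because it mixes in the patients who by rule receive none.

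What is at stake is what may be concluded. A report could cite 9.1 as a prespecified aim to show benefit and support it with an unplanned split by local therapy ever received. Section 2.1 leaves an opening for such a split: it asks for OS in each treatment cohort, and 3.1 labels the design parallel-group, but the readable text defines no cohort.

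**Working it through.** **1. The texts side by side.** The first paragraph of 9.1 is confirmatory. The second paragraph of 9.1 and the text under 10.2 are descriptive, 2.1 evaluates and Section 1 explores. The analysis in 9.2.3 fits the descriptive wording and cannot meet the confirmatory one. The stated sample size of about 100 cannot be reproduced, because 9.1 says it rests on no statistical assumptions. The only arithmetic available is 100 × (1 − 0.20) = 80 after the stated minimum dropout.

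**2. Events (illustration).** Assumed proxy: the lorlatinib PFS quoted in Section 1, namely 78%, 68.2% and 63.5% at 12, 24 and 36 months.

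- Exponential through 36 months: hazard = −ln(0.635)/36 = 0.0126 per month, so S(60) = 0.469 and 100 patients give 53.1 events.
- Piecewise through the three points, last hazard carried on: ln(0.682/0.635)/12 = 0.00595 per month, so S(60) = 0.635 × exp(−24 × 0.00595) = 0.550 and 100 patients give 45.0 events.
- If 20% drop out and contribute none: 0.8 × 53.09 = 42.47 and 0.8 × 44.95 = 35.96.

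These counts are not firm. Sections 3.1 and 5.1 list withdrawal and loss to follow-up among the ends of treatment, so dropouts may count as events. Section 3.1 also allows lorlatinib beyond progression, which may lower the count.

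**3. What a comparison would need.** Detectable HR at 80% power, two-sided 5% = exp(−2.8016/√(p(1−p)d)), with p the share given local therapy (assumed) and d the events.

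| Split | d = 53.1 | d = 36.0 |
|---|---|---|
| 1:1 | 0.46 | 0.39 |
| 30:70 | 0.43 | 0.36 |

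**4. What description can deliver.** 95% CI half-width for a 36-month rate of 63.5% = 1.96 × √(0.635 × 0.365/n): 9.4 points for n = 100 and 10.5 for n = 80.

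**5. Why a split from first dose would mislead.** A patient must stay on lorlatinib until the second stable scan to receive local therapy, so that group has guaranteed event-free time. Section 3.1 schedules scans at week 4 and then every 8–12 weeks: weeks 12–16 and 20–28. With the ±2 weeks of Section 6, these become weeks 10–18 and 18–30, according to whether the week-4 scan counts. Simulated TTD hazard ratios (ever versus never, no true effect, prognostically alike groups, 60 months of follow-up), for assumed uptake of 30% and 70%:

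| Curve | Week 10–18 | Week 18–30 |
|---|---|---|
| Exponential | 0.90, 0.79 | 0.83, 0.68 |
| Three-point | 0.81, 0.65 | 0.70, 0.51 |

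Week 30 is not an upper bound, since 6.2.4 sets no deadline. Local therapy at week 30–52 takes the lowest value to about 0.36.

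**6. Cost of a sounder contrast.** Assume 60 of 100 patients are eligible. Events after time t = 60 × (S(t) − S(60)).

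- From the second stable scan: 30.1 (exponential, week 10) to 19.0 (three-point, week 30); with 20% dropout, 24.1 to 15.2.
- From a landmark 8 weeks after the window closes: 27.5 (exponential, week 26) to 17.0 (three-point, week 38); with 20% dropout, 22.0 to 13.6.

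With a 1:1 split, the 95% CI is the HR multiplied or divided by exp(1.96 × 2/√d): 2.04 at d = 30.1 and 2.89 at d = 13.6.

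**The case against.** The other side can say that the fault is one sentence. Section 2.1, the Introduction, the second paragraph of 9.1 and the text under 10.2 are all softer than *demonstrate*, and the operative analysis agrees with them. That is right, and it is why rewording is enough.

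Three limits on the reading also stand.

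- Section 9.2.3 names no population for TTD. All-treated is inferred, because the safety set is the only one defined, and 9.2.1 makes it primary only for compliance and safety.
- The study design figure is not shown and may label cohorts, and the subgroup list in 9.2.5 is open-ended. So the claim is that the readable text specifies no TTD contrast by local therapy, not that no grouping exists anywhere.
- An SAP could define groups and methods. It could not reconcile an objective to demonstrate with a statement that nothing is tested.

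A reader might infer more than the protocol supports. One inference is that the primary analysis is biased by guaranteed event-free time. It is not, since no split of TTD by local therapy is planned; the bias arises only if one is made. Another is that any such split must favour local therapy. That does not follow: the group without it would include complete responders as well as patients with multiple metastases, so differing prognosis can cancel or reverse the bias. A third is that 100 patients are too few. For a descriptive study no power is claimed, and the detectable hazard ratios show low power for a comparison, not an error in the stated sample size.

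**Conclusion.** The contradiction rests on the text alone and should be fixed. The primary objective as worded in 9.1 conflicts with the protocol's own descriptive declaration, and the analysis in the readable text cannot deliver it. A missing cohort label in the design figure would not change that.

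The sizes are illustrations. They rest on PFS standing in for TTD, on combining rates from two data cutoffs, and on assumed uptake, timing and eligibility. Under those assumptions the study suits description (about ±9 to 11 points at 36 months) far better than demonstration (HR of about 0.36–0.46 needed). A split from first dose could show an HR of about 0.9 to 0.5 with no effect at all, or lower if local therapy comes later. That range applies only to prognostically alike groups and does not predict results.

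**What to change.** 1. In 9.1, replace the demonstrate-prolongation wording with an objective to describe TTD. Align the Introduction and 2.1, and state which patients the primary TTD describes.
2. In 9.2.3 and 9.2.5, state that any curves by local therapy from first dose are descriptive and not evidence of effect. This includes OS by treatment cohort, if cohorts mean local therapy yes or no; say what the cohorts are.
3. Add one sentence: if a contrast by local therapy is reported, it uses time-dependent local-therapy status, or a fixed landmark with exposure classified up to that point. Either is limited to patients still on lorlatinib who met the protocol's criteria of partial response or stable disease with oligometastasis. Details go to the SAP.

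Items 1 and 2 cost wording only, with no new patients or data. Item 3 costs precision: if 60 of 100 patients are eligible, about 14–30 TTD events remain, depending on method and dropout, and the 95% CI is the HR multiplied or divided by about 2.0–2.9. Confounding by selection for local therapy would remain, so such a contrast would still not demonstrate prolongation. If the sponsor wants to keep the comparative aim, it would have to define the groups and justify the sample size for that purpose.

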9.2 Effectiveness Analysis

9.2.1 Analysis Populations

The following subject populations will be assessed:

Safety-Analysis-Set (SAT) Population

The SAT Population will include all subjects who receive at least 1 dose of study medication. The SAT Population will be the primary population for evaluating treatment administration/compliance and safety.

Censoring for time-to-event efficacy endpoints (i.e., PFS and OS) will be elaborated in the SAT.

9.2.2 Definition of Primary Endpoint

Time-to treatment discontinuation (TTD) is defined as the time from start of treatment to the date of discontinuation of lorlatinib.

9.2.3 Analysis of Primary Endpoint

TTD will be summarized using Kaplan-Meier methods and displayed graphically. Potential influences of other demographic baseline characteristics including biomarker profile use parametrical test, χ^2 or Fisher exact test .

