initiation) in patients with previously untreated advanced ALK-positive NSCLC.²² At the time of first data cutoff, the mPFS was not reached (NR; 95% confidence interval [CI], NR=NR) in the lorlatinib group, as compared with 9.3 months (95% CI, 7.6-11.1) in the crizotinib group by BICR. The percentage of patients who were alive without disease progression at 12 months was 78% in the lorlatinib group and 39% in the crizotinib group (hazard ratio, 0.28, 95% CI, 0.19-0.41); $P < 0.001$, one-sided). The hazard ratio favored lorlatinib over crizotinib across all prespecified patient subgroups defined according to baseline characteristics and stratification factors. At the second data cutoff, the mPFS was yet NR (95% CI, NR-NR) in the lorlatinib group, as compared with 9.3 months (95% CI, 7.6-11.1 months) in the crizotinib group by BICR.²² 24-month and 36-month PFS rate were distinctly higher in the lorlatinib group of 68.2% and 63.5%, as compared with 21.5% and 18.9% in the crizotinib group (hazard ratio, 0.27, 95% CI, 0.184-0.388). For patients with measurable brain metastases at baseline, lorlatinib achieved 72% intracranial complete response (CR) rate, and 83% intracranial objective response rate (ORR). Time to intracranial progression by BICR was remarkably longer with lorlatinib than crizotinib in the intention-to-treat population as well as in patients with and without baseline brain metastases, in which 8 out of 37 patients with baseline brain metastases and only 1 out of 112 patients without baseline brain metastases had intracranial progression after median follow-up over 36 months. This indicates that lorlatinib possesses the potential to clear existing brain metastases, meanwhile prevents new metastatic lesions in the brain.

In consideration of high intracranial activity and 63.5% PFS rate and not reached mPFS after 36.7 months follow-up in the CROWN trial,²² ALK-positive NSCLC patients shall benefit most using lorlatinib in the first-line treatment in the clinical practice. Nevertheless, only 10 ALK+ NSCLC patients were randomized to the lorlatinib group in China mainland, and published data of clinical trials regarding first-line treatment of lorlatinib is still limited to CROWN trail. There is a vast vacancy of efficacy and safety regarding first-line lorlatinib treatment in China ALK-positive NSCLC patients. Further,

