10.2 Trial Management Committee

The Trial Management Committee will oversee study planning, monitoring, progress, review of information from related research, and implementation of recommendations from other study committees and external bodies (e.g. ethics committees).

Selection Bias: Real-world study population is relatively unselected compared with randomized clinical trials in terms of stringent inclusion and exclusion criteria.

However, selection bias still exists because the participants are not randomly drawn from the target population. First, patients will be recruited from particular sites that are characterized by the site's prevalent demographics, specific routine clinical practice procedures, and the different levels of experience in the investigators.

Second, there is also selection bias due to loss to follow up (also known as informative censoring), which often happen when a patient can no longer be tracked due to various reasons such as hospital referral or migration.

Information Bias: Information bias due to missing data exists in almost all kinds of studies. In contrast to the prospective clinical trials, where study variables are intentionally prespecified and collected, the availability, completeness of the data in this study requires special attention since the data is originally recorded without any intervention to prevent missingness.

Generalizability: While the real-world study can include a wider population than randomized control studies, the generalizability of this study may still be affected by the geographic location of the sample study population and hospital specific characteristics and may lead to differences in variations in outcomes. The analysis

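### Protocol 9.2.3 tests factor effects on right-censored TTD with parametric, chi-square or Fisher tests; 9.2.5 repeats this beside a log-rank rule and does not reconcile the two

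*Protocol*

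**What the plan says.** Section 9.2.2 defines TTD, the primary endpoint, as the time from starting treatment to stopping lorlatinib. Section 9.2.3 deals with TTD alone. It calls for Kaplan-Meier summaries and then states: "Potential influences of other demographic baseline characteristics including biomarker profile use parametrical test", chi-square or Fisher's exact test. It names no log-rank test, Cox model or parametric survival model.

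Section 9.2.5 has nearly the same sentence, "Potential influences of other demographic, baseline characteristics including biomarker profile use parametrical test". It stands directly after the Kaplan-Meier text for rwPFS, IC-TTP and OS and directly before the text on objective response. Further on, 9.2.5 names CNS metastases, TP53 status and ALK-EML4 variant as subgroup factors and says: "Subgroup comparisons, where is applicable, will be performed using the Kaplan-Meier method and the log-rank test". It sets a two-sided level of 0.05 for tests.

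Section 2.1 includes a secondary objective "To explore the association between the effectiveness of lorlatinib in first line for Chinese patients" and brain metastases, ALK fusion variant and TP53 status. Section 10.2 says that "no hypotheses will be tested in this study and only descriptive analysis will be performed".

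**The concern.** Summarising TTD by Kaplan-Meier accepts that it is right-censored, yet the tests named in the next sentence do not use that information. Chi-square and Fisher compare the proportions with an observed event and ignore both when events occurred and how long each patient was at risk. A t-type test on observed times treats a patient still on lorlatinib at last contact as if treatment had stopped that day.

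Section 9.2.5 adds a conflict. A biomarker profile would include TP53 and ALK variant, so these factors fall under both the parametric/chi-square/Fisher sentence and the log-rank sentence, and nothing says which governs which endpoint. The log-rank rule is under the secondary-endpoints heading and does not mention TTD.

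At stake are lower power to see a real association with the primary endpoint and, if follow-up differs between factor levels, spurious associations.

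**Working it through.** **Reading the text.** TTD is the only endpoint in 9.2.3, so chi-square and Fisher cannot be meant there for a response rate. In 9.2.5 they could be meant for objective response, where they would be suitable, so the scope is unclear.

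**Inputs from the protocol.** About 100 patients and "at least 20% dropout rate" (9.1); follow-up to 60 months (3.1); two-sided 0.05 (9.2.5); 36-month lorlatinib PFS of 63.5% in the cited phase 3 trial (Introduction).

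**Assumptions.** That PFS rate stands in for TTD, although 3.1 allows lorlatinib beyond progression. Times are exponential, the factor splits 50:50, and dropout is exponential and independent within each group. The hazard ratio (HR) of 2 and any difference in dropout by factor level are illustrative. The protocol has no power figure to reproduce.

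**How much is censored.**
- Hazard: λ = −ln(0.635)/36 = 0.0126 per month. Still on treatment at 60 months without dropout: exp(−60λ) = 46.9%.
- 20% dropout by month 60: δ = −ln(0.80)/60 = 0.0037 per month.
- Share with an observed event: λ/(λ+δ) × [1 − exp(−60(λ+δ))] = 0.772 × (1 − 0.469 × 0.80) = 0.48. About 52% are censored.

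**Rejection rates (%), 10,000 simulated trials per row.** Chi-square has no continuity correction; the t-test is pooled-variance on observed times. Two versions of HR 2 are used: (a) the better group has λ = 0.0126; (b) the groups have 0.00863 and 0.01726 per month, averaging 63.5% at 36 months.

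| Scenario | Chi-square | Fisher | t-test | Log-rank |
|---|---|---|---|---|
| No effect, dropout 20% v 20% | 5.5 | 3.3 | 4.8 | 4.7 |
| No effect, dropout 10% v 30% | 9.0 | 6.0 | 15.2 | 4.8 |
| No effect, dropout 10% v 40% | 13.7 | 9.5 | 30.2 | 5.0 |
| HR 2 (a), dropout 20% v 20% | 68.5 | 61.2 | 62.3 | 76.6 |
| HR 2 (b), dropout 20% v 20% | 64.4 | 56.8 | 49.2 | 66.4 |
| HR 2 (a), 40% dropout in the worse group, 10% in the other | 31.5 | 24.6 | 92.9 | 75.1 |
| HR 2 (b), 40% dropout in the worse group, 10% in the other | 32.1 | 25.3 | 91.2 | 65.1 |

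**Loss against log-rank at equal dropout.** Chi-square: 76.6 − 68.5 = 8.1 and 66.4 − 64.4 = 2.0 points. Fisher: 15.4 and 9.6. t-test: 14.3 and 17.2.

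**Cross-check.** Version (a) gives about 60 events. Schoenfeld's formula gives Φ(√60/2 × ln 2 − 1.96) = Φ(0.72) = 77%, in line with the simulated 76.6%.

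In the last two rows, the t-test's 91-93% is bias, not power: early loss in the worse group is counted as early discontinuation.

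**The case against.** The strongest reply is that most of this is already covered. The association objective concerns brain metastases, ALK variant and TP53, which are the factors that 9.2.5 gives to log-rank. Section 9.2.5 also holds study-wide rules, such as interim and final analysis timing, so its log-rank sentence might be meant for TTD too. This narrows the gap to TTD and to factors outside those three. It does not remove it: 9.2.3 states its own method for TTD, and nothing in 9.2.5 overrides it.

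A parametric test could mean a parametric survival model. The text does not say so, and that reading would not rescue chi-square or Fisher. It does mean that the t-test figures rest on one reading of a loose phrase.

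The inflated error rates depend on assumed dropout differences. That stands. Section 10.2 warns that "there is also selection bias due to loss to follow up (also known as informative censoring"), but gives no loss by factor level. Truly informative censoring would also bias log-rank and Cox, so that warning does not by itself favour the repair.

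The censoring may also be lighter than assumed. Sections 3.1 and 5.1 list loss to follow-up among the reasons lorlatinib ends, so it might count as a TTD event. With censoring only at 60 months, at HR 2 chi-square has 75.6% power against 80.3% for log-rank in version (a), and 69.8% against 69.5% in (b). Chi-square then loses 0-5 points, Fisher 7-12 and the t-test about 5-10.

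Finally, the study is descriptive and unpowered. That limits the consequence, but 9.2.5 still sets a 0.05 level, so p-values will be produced and read.

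**Conclusion.** The concern holds. Section 9.2.3 names tests unsuited to its right-censored primary endpoint, and 9.2.5 leaves two rules for overlapping factors unreconciled. This is a stated method, not detail left to a SAP: a SAP that followed 9.2.3 would carry the error forward, and one that used log-rank would depart from the protocol.

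Under the stated assumptions (PFS as proxy for TTD, exponential times, equal 20% dropout, HR 2), log-rank power is 66-77%, against 64-69% for chi-square, 57-61% for Fisher and 49-62% for the t-test. Type I error is not materially inflated in that setting. At an assumed 10% v 40% dropout it reaches about 14%, 10% and 30% respectively, while log-rank stays at 5%. No confirmatory conclusion depends on this, but it affects the primary endpoint and should be corrected before analysis.

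**What to change.** In 9.2.3 and 9.2.5, replace the sentence on potential influences with:

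> Associations of baseline and biomarker factors with TTD, rwPFS/TTP, IC-TTP and OS will use log-rank tests and Cox regression (hazard ratio, 95% CI). Chi-square or Fisher exact tests will be used only for binary endpoints (ORR, DCR, IC-ORR).

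State that the log-rank rule in 9.2.5 also covers TTD, and label the p-values exploratory, in line with the descriptive aim in 9.1 and 10.2.

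The cost is one sentence in each of two sections and a short clarification. The data, patients and visits are unchanged, and the software is standard.
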